4. STUDY DESIGN

4.1. Primary and Secondary Outcomes

According to the aim and objectives of this study, safety and efficacy of Polyoxidonium®, lyophilizate for solution for injections and topical application, 6 mg (NPO Petrovax Pharm LLC, Russia) will be evaluated in hospitalized patients with coronavirus disease (COVID-19).

Efficacy outcomes

Primary efficacy outcome

Subject clinical status using the WHO 7-point ordinal scale on day 15 as compared to baseline.

1. Not hospitalized, no limitations on activities.
2. Not hospitalized, limitation on activities.
3. Hospitalized, not requiring supplemental oxygen.
4. Hospitalized, requiring supplemental oxygen.
5. Hospitalized, on non-invasive ventilation or high flow oxygen devices.
6. Hospitalized, on invasive mechanical ventilation or ECMO.
7. Death.

Secondary efficacy outcomes

Clinical severity assessed by scales

1. Subject clinical status using the WHO 7-point ordinal scale

- Time to improvement of each parameter of the primary scale from admission.

- Subject clinical status at days 3, 5, 8, 11, and 29.
 - Average change in the clinical status at days 3, 5, 8, 11, 15, and 29 as compared to baseline.
2. *The NEWS Score (National Early Warning Score) describes the vital signs (pulse rate, breathing rate, temperature, blood pressure etc.) and its deviation from the reference ranges):* is evaluated daily and on day 15.
- The time to discharge or to a NEWS of ≤ 2 and maintained for 24 hours, whichever occurs first.
 - Change from baseline to days 3, 5, 8, 11, 15, and 29 in NEWS.
3. *Oxygenation, including mechanical ventilation:*
- Change (day by day) in the need for oxygenation in the first 28 days (up to day 29).
4. *Hospitalization*
- Duration of hospitalization (days).
5. *Mortality (date, cause)*
- 28-day mortality.
6. *SOFA scale (evaluation of organ failure associated with sepsis):* is evaluated daily and on day 15.
- Change from baseline to days 3, 5, 8, 11, 15, and 29 in SOFA.

Safety outcomes

Safety outcomes

- Cumulative incidence of serious adverse events/reactions (SAEs, SARs)
- Cumulative incidence of adverse events/reaction (AEs, ARs)
- Permanent or temporary discontinuation of infusions/injections (by any cause)
- Clinically significant changes in the levels of leukocytes, haemoglobin, platelets, creatinine, glucose, total bilirubin, ALT, AST, CRP, and other parameters.

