4.2. Type/design of the study

This study is an open multi-centre observational study evaluating the efficacy and safety of a non-interventional drug.

The design of a non-invasive non-interventional study was chosen to evaluate the efficacy of the drug in routine clinical practice. Since this study will be non-interventional, all procedures will be carried out in strict accordance with the standards of routine clinical practice and meet the non-interventional criteria set by the Good Pharmacovigilance Practice of the Eurasian Economic Union [approved by the decision of the Council of the Eurasian Economic Commission dated 03.11.2016 No. 87].

No	CRITERION	CONTENT
1	Object, MA	Drug products approved for human use; with a valid marketing authorization
2	Rationale for prescription	As judged by the doctor within the routine clinical practice
3	Time of prescription	Prior to inclusion in the study and regardless of the decision to participate
4	Requirements to the prescription	According to the approved therapeutic indications (therapeutic indications, dosage, etc.)

According to the current routine practice, up-to-date and widely accepted

5	Patient management	clinical guidelines and guides According to the protocol, however, the intervention in the routine management of the patient is minimal
6	Randomization, blinding	Not applicable

The clinical efficacy will be assessed by changes in the patient’s clinical status, duration of hospitalization, oxygenation/mechanical ventilation. The clinical examination will include clinical, laboratory, and instrumental investigations according to the current guidelines on treatment of COVID-19 in the Russian Federation. No additional procedures, except for the special scales (non-invasive), will be carried out during the planned non-interventional study.

The overall objective of the study is to evaluate the clinical efficacy of the investigational product in adult patients hospitalized with COVID-19. The primary endpoint is the patient’s clinical status (in a 7-point ordinal school) on day 15 in accordance with the WHO Master Protocol¹.

The study will be conducted in the clinical centre during hospitalization and outpatient visits of patients to the clinical centre, if necessary.

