6.3.5. Laboratory tests

The schedule of laboratory tests is included in description of the study parts and in the schedule of the study procedures.

List of the evaluated laboratory parameters

¹ Temporary guidelines. Prevention, diagnosis, and treatment of the novel coronavirus infection (2019-nCoV). Version 2 (02/03/2020). Electronic source with free access: <https://static-i.rosminzdrav.ru/system/attachments/attaches/000/049/329/original/%D0%92%D1%80%D0%B5%D0%BC%D0%B5%D0%BD%D0%BD%D1%8B%D0%B5%D0%9C%D0%A0%2019-nCov%2003.02.2020%28%D0%B2%D0%B5%D1%80%D1%81%D0%B8%D1%8F%29%29%20final.pdf?1580748451>.
Access date: March 16, 2020.

Haematology

Red blood cells, haematocrit, white blood cells, platelets, neutrophils, eosinophils, basophils, monocytes, lymphocytes

The volume of the blood sample is approximately 5 mL.

Blood chemistry

Urea, creatinine, Na⁺, K⁺, bilirubin, glucose, ALT, AST, albumin, pH, bicarbonates, lactate, coagulogram with prothrombin time, coagulogram with international normalized ratio and activated partial thromboplastin time, CRP. The blood sample volume is approximately 5 mL.

If indicated: PaO₂, FiO₂, PaCO₂

Urinalysis

According to routine practice of the centre.

Test for SARS-CoV-2

The test is performed at the screening to assess the eligibility. Data obtained not later than 48 hours before signing the informed consent may be used.

Oropharyngeal/nasal (OP/N) sample

Oropharyngeal/nasal samples will be taken in accordance with the routine practice of the health care institution.

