9.4. Drop-outs, withdrawn patients, and missing data

No missing data will be substituted. The missing/omitted data will not be considered during statistical analysis.

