16. APPENDICES

SCHEDULE OF ASSESSMENTS

Table 1. Study plan
(ALL THESE PROCEDURES SHOULD BE CARRIED OUT IN THE FRAMEWORK OF ROUTINE PRACTICE OF THE HEALTH CARE INSTITUTIONS)

Procedure / days	Study according to the Protocol No. COVID dated March 30, 2020				
	Day 1	Daily (up to discharge ^{***})	Day 3, 5, 7, 11	Day 15±1	Day 29±3 or any other last day ^{****} of the study
Enrolment criteria	X				
Withdrawal criteria		X	X	X	X
Informed consent, enrolment	X				
Polyoxidonium	10 doses: days 1, 2, 3, 5, 7, 9, 11, 13, 15, 17				
History	X				
Clinical signs and symptoms, physical examination¹	X	X	X	X	X
Nasopharyngeal and/or oropharyngeal smear	X		X	X	X
Haematology²	X**		X	X	X
Blood chemistry³	X**		X	X	X
CRP	X**		X	X	X
Urinalysis⁴	X**		X	X	X
Bacteriological inoculation of sputum	If necessary				
Chest X-ray/ CT*	If indicated				
ECG*	If indicated				
SpO₂⁵	X	X	X	X	X
Evaluation of need for oxygenation, including mechanical ventilation	X	X	X	X	X
Assessment of the treatment efficacy⁶	X	X	X	X	X
Assessment of safety	X	X	X	X	X
NEWS Score	X	X	X	X	X
SOFA Score	X	X	X	X	X
Clinical status by WHO scale	At admission	X	X	X	X

Notes to Table 1

*- including at admission, before enrolment

** - results of the previous laboratory investigations within 48 hours before enrolment can be used

*** - visits to the clinic are preferred after discharge, but the quarantine or other reasonable factors can limit this opportunity. The visits could be performed in a form of phone call or with other remote communication technologies. Some data will not be collected by obvious reasons.

**** - in case of the patient withdrawal (see the withdrawal criteria)

1 – Clinical signs and symptoms

Weakness, fatigue, cough, shortness of breath, stuffiness in the chest, myalgia, headaches, haemoptysis, palpitations, nasopharyngeal symptoms, diarrhoea, nausea, vomiting; physical

examination: heart rate, blood pressure, respiratory rate, body temperature

2 – Haematology

Red blood cells, haematocrit, white blood cells, platelets, neutrophils, eosinophils, basophils, monocytes, lymphocytes

3 - Blood chemistry

Urea, creatinine, Na⁺, K⁺, bilirubin, glucose, ALT, AST, albumin, pH, bicarbonates, lactate, coagulogram with prothrombin time, coagulogram with international normalized ratio and activated partial thromboplastin time, CRP

If indicated: PaO₂, FiO₂, PaCO₂

4 – Urinalysis

According to routine practice of the centre

5 - SpO₂

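### SOFA change has no scheduled laboratory inputs on Day 8 and relies on blood gases taken only if indicated, with no rule for scoring without them

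*Combined protocol and SAP*

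**What the plan says.** Section 4.1 (repeated in the Synopsis and Section 7.1) makes SOFA the sixth secondary efficacy outcome. It "is evaluated daily and on day 15", and the analysed quantity is "Change from baseline to days 3, 5, 8, 11, 15, and 29 in SOFA". Table 1 in Section 16 marks SOFA in every column, including the daily column that runs up to discharge.

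The inputs follow a different timetable. In Table 1, haematology and blood chemistry are blank in the daily column and marked on Day 1, on Days 3, 5, 7 and 11, on Day 15±1 and on Day 29±3. For Day 1, "results of the previous laboratory investigations within 48 hours before enrolment can be used". Blood gases are conditional on every day: Section 6.3.5 and the notes to Table 1 give "If indicated: PaO₂, FiO₂, PaCO₂".

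Three other provisions bear on this. Section 4.2 states "No additional procedures, except for the special scales (non-invasive), will be carried out during the planned non-interventional study". Section 9.4 states "No missing data will be substituted" and leaves missing values out of the analysis. Section 9.7.2 makes ITT the main efficacy population. Section 6.3.8 prints a full scoring table for NEWS. For SOFA it gives only a general description, with no components and no rule for an unmeasured component.

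**The concern.** A multi-component score can be computed only when all its components are available, or when a rule says what to do if one is not. Here the score and its inputs are scheduled separately, one input depends on clinical indication, and no such rule exists.

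Two things are at stake. The first is coverage: scores are requested on days with no scheduled laboratory results, including one of the analysis days. The second is selection. If a complete score needs a clinically triggered blood gas, availability of the endpoint may depend on how ill the patient is, at baseline and again at follow-up. A recovering patient whose gases are no longer checked would drop out of the change analysis. The result would then describe a subset, although the plan names ITT. Alternatively, centres may fill the gap each in their own way, for example by scoring an unmeasured component as normal, which could create apparent improvement at follow-up. With a single group, no comparator would reveal either distortion.

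**Working it through.** The plan states no SOFA figure, power or effect size, so there is nothing to reproduce. The check is a comparison of dates followed by an illustration.

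**Step 1: dates.** Laboratory days in Table 1: 1, 3, 5, 7, 11, 15, 29. SOFA analysis days in Section 4.1: 3, 5, 8, 11, 15, 29, each against baseline.

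- Analysis days with scheduled laboratory tests: 3, 5, 11, 15, 29, which is 5 of 6. Baseline is also covered.
- Analysis day without: Day 8, which is 1 of 6. Table 1 has Day 7 instead and prints windows only for Days 15 and 29, so Day 7 results do not count as Day 8 by any stated window.
- For daily scoring, laboratory tests are scheduled on 6 of the 17 treatment days, or 7 of Days 1 to 29.

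**Step 2: components.** Assume the standard SOFA components, since the protocol prints none. Platelets, bilirubin and creatinine come from the scheduled panels. Blood pressure and level of consciousness are already collected for NEWS. The respiratory component is PaO2/FiO2, which is guaranteed on no day. SpO2 is scheduled at every visit and daily, but nothing says that it may stand in for PaO2.

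**Step 3: illustration of selection.** The documents give neither the severity mix nor the frequency of blood gases, so every input here is an assumption except N = 50, the stated minimum. Let *s* be the severe share, and let *p_s* and *p_m* be the proportions of severe and mild-moderate patients with the blood gases needed for a complete change score.

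Complete = 50 × [*s·p_s* + (1 − *s*)·*p_m*]

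Severe share of complete = *s·p_s* / [*s·p_s* + (1 − *s*)·*p_m*]

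| *s* | *p_s* | *p_m* | Complete of 50 | Severe share |
|---|---|---|---|---|
| 0.3 | 0.5 | 0.05 | 9.2 | 81% |
| 0.3 | 0.5 | 0.2 | 14.5 | 52% |
| 0.3 | 0.9 | 0.05 | 15.2 | 89% |
| 0.5 | 0.5 | 0.2 | 17.5 | 71% |
| 0.5 | 0.9 | 0.05 | 23.8 | 95% |
| 0.7 | 0.9 | 0.05 | 32.2 | 98% |
| 0.7 | 0.9 | 0.2 | 34.5 | 91% |
| 0.5 | 0.3 | 0.3 | 15.0 | 50% |

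Where *p_s* exceeds *p_m*, the severe share of complete scores exceeds the severe share enrolled. In the last row gases are taken equally often in both groups: data are lost, but there is no selection on severity.

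**The case against.** Four objections have force.

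First, a reader might take 7 laboratory days out of 29 as the size of the damage. That count applies to daily scores, and no listed outcome analyses SOFA day by day. For the change endpoint the laboratory schedule costs one day of six. This stands.

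Second, a reader might infer that complete scores will exist mainly, or only, for the sickest patients. The documents do not say this. It needs the standard respiratory component, which is not printed, and blood gases that are rarer in milder patients, which is not stated or quantified. Moreover, pH, bicarbonate and lactate are in the chemistry panel for everyone, so some gas analysis may be done in milder patients too, although that does not show that PaO2 is recorded. The inference is plausible because Section 5.1 admits mild-moderate patients without oxygen, but it remains conditional.

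Third, Table 1 is not shown to be a ceiling. Care is routine, and Section 6.2 lists haematology and chemistry for Days 2 to 18 without dates. That section defers to Appendix 1, where the daily column is blank. So extra results may exist but are not guaranteed, and it would be too strong to say that daily scores cannot be completed.

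Fourth, Section 9.4 bars substitution of missing data. Scoring a component from recorded SpO2 can fairly be called a scoring convention, on which the plan is silent. It would therefore be wrong to say that the plan forbids it, but equally nothing authorises it, and centres could differ.

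None of this removes the mismatch of days or the absence of a scoring rule.

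**Conclusion.** The point holds in a limited form. From the documents alone, daily SOFA is not supported by the laboratory schedule, Day 8 has no scheduled laboratory inputs, PaO2/FiO2 is assured on no day, and no rule covers an incomplete score.

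Conditional on the standard PaO2/FiO2 component and on more frequent blood gases in sicker patients, complete SOFA-change data would over-represent severe patients relative to ITT. The illustrative range, about 9 to 35 complete of 50 with 52% to 98% severe, shows how far this depends on unknown practice and is not an estimate.

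A separate cause of gaps is stated outright: Section 6.2 and the notes to Table 1 allow remote visits after discharge and accept that some data will not be collected, which can affect any SOFA score due after discharge.

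SOFA is a secondary endpoint. The primary seven-point scale needs no laboratory or blood-gas input and is unaffected. The change is worth making because it is cheap, but the study's main result does not depend on it.

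**What to change.** - Restrict SOFA to the scheduled laboratory days and drop the daily requirement in the Synopsis, Sections 4.1 and 7.1 and Table 1. Reconcile Day 7 with Day 8 across the same places. Using Day 7 for SOFA would need no change to the laboratory schedule.
- Print the SOFA components and scoring in Section 6.3.8, as is done for NEWS.
- Prespecify that the respiratory component is scored from SpO2/FiO2 when no blood gas is available. FiO2 is 0.21 on room air. For patients on oxygen, FiO2 is itself collected only if indicated, so the eCRF must record delivered oxygen. State in Section 9.4 that this is a scoring rule and not imputation.
- Map consciousness from the recorded AVPU letter and not from the NEWS points, because V, P and U all score 3 and the points cannot grade impairment. Print the mapping.
- Report the number of complete SOFA scores by day and baseline severity, and how many respiratory scores used SpO2. State that scores after discharge may still be missing when visits are remote, since a call yields no laboratory result and may yield no SpO2.

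The cost is protocol and SAP wording plus an eCRF field for delivered oxygen; no new test is needed. The surrogate respiratory score is less exact than one based on PaO2, and the documents give no basis for saying by how much.

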4.2. Type/design of the study

This study is an open multi-centre observational study evaluating the efficacy and safety of a non-interventional drug.

The design of a non-invasive non-interventional study was chosen to evaluate the efficacy of the drug in routine clinical practice. Since this study will be non-interventional, all procedures will be carried out in strict accordance with the standards of routine clinical practice and meet the non-interventional criteria set by the Good Pharmacovigilance Practice of the Eurasian Economic Union [approved by the decision of the Council of the Eurasian Economic Commission dated 03.11.2016 No. 87].

No	CRITERION	CONTENT
1	Object, MA	Drug products approved for human use; with a valid marketing authorization
2	Rationale for prescription	As judged by the doctor within the routine clinical practice
3	Time of prescription	Prior to inclusion in the study and regardless of the decision to participate
4	Requirements to the prescription	According to the approved therapeutic indications (therapeutic indications, dosage, etc.)

According to the current routine practice, up-to-date and widely accepted

5	Patient management	clinical guidelines and guides According to the protocol, however, the intervention in the routine management of the patient is minimal
6	Randomization, blinding	Not applicable

The clinical efficacy will be assessed by changes in the patient’s clinical status, duration of hospitalization, oxygenation/mechanical ventilation. The clinical examination will include clinical, laboratory, and instrumental investigations according to the current guidelines on treatment of COVID-19 in the Russian Federation. No additional procedures, except for the special scales (non-invasive), will be carried out during the planned non-interventional study.

The overall objective of the study is to evaluate the clinical efficacy of the investigational product in adult patients hospitalized with COVID-19. The primary endpoint is the patient’s clinical status (in a 7-point ordinal school) on day 15 in accordance with the WHO Master Protocol¹.

The study will be conducted in the clinical centre during hospitalization and outpatient visits of patients to the clinical centre, if necessary.

Patients who meet the inclusion criteria and do not meet any of the exclusion criteria will be included in a single study group, that will receive Polyoxidonium®, lyophilizate for solution for injections and topical application, 6 mg (NPO Petrovax Pharm LLC, Russia) in dose of 12 mg once daily intravenously (IV) for 3 days, then every other day intramuscularly (IM) on days 5–17 (the total treatment course is 10 injections).

The data collected in this observational program should help doctors find more effective therapy for other patients with COVID-19.

The study will include the following periods:

- **Treatment period** (17 days in total, days 1...17, if the study criteria are met) with administration of the investigational product (IP) (intravenous injections for 3 days, then intramuscular injections for 14 days), assessment of the clinical status, recording of AEs.

- **Follow-up period** (days 18...29±3)

Figure 4.1 shows the study flow chart.

[figure not shown]

Figure 4.1. Study flow chart

¹ MASTER PROTOCOL. A Multi-centre, Adaptive, Randomized, Double-Blind, Placebo-Controlled Clinical Trial of the Safety and Efficacy of Investigational Therapeutics for the Treatment of COVID-19 in Hospitalized Patients. Electronic source Free access: <https://www.who.int/blueprint/priority-diseases/key-action/multicenter-adaptive-RCT-of-investigational-therapeutics-for-COVID-19.pdf>. Access date: March 13, 2020

4.3 Measures that minimise/eliminate subjectivity during the study

The study limitations are typical for an observational study. The inclusion criteria were set so that the analysed population is representative of the target group of patients and allows to generalize the findings. Such design should prevent a systematic selection error that may occur if the patients are enrolled depending on a recorded outcome. The study plans to include a relatively large number of centres in various countries. Such international multicentre studies have the advantage of being able to generalize the results to a population of interest. All the necessary data will be collected at the enrolment visit and all subsequent visits to minimize errors associated with missing data. Also, such prospective observational study might include a systematic error related to patient withdrawal. However, all possible latest data and the reason for the discontinuation will be collected in case of a patient discontinuation.

4.3.1. Blinding

In contrast to interventional clinical trials, the design of non-interventional trials does not involve randomization and blinding. In accordance with the non-intervention principle, the doctor's decision to prescribe a therapy is made before the patient is included in the study as part of routine clinical practice and in no way can be associated with the possibility of the patient participating in this study. As a result, blinding is impossible. The procedures will be carried out within the current routine clinical practice in the presence of relevant therapeutic indications.

4.3.2. Randomization

Not applicable.

4.4 Expected duration of a patient's participation in the study

The total duration of a patient's participation in this study will not exceed 32 days.

The study will include the following periods:

- **Treatment period** – administration of IP, evaluation of the clinical status, recording of AEs.
- **Follow-up period** – evaluation of the clinical status, recording of AEs.

4.5. Suspension, termination of the study, withdrawal of the study subjects

The Sponsor may suspend the study at any time based on any reasons that include, but are not limited to, safety, ethics, or administrative issues.

The Sponsor can terminate the study at any time if the aim and objectives of the study are not met.

The Sponsor should inform the investigator or the leadership of the study centre about the study suspension or termination in writing.

If the study is suspended or terminated because of a safety issue, the Sponsor shall notify the Investigator, regulatory authorities, and the ethics committees immediately.

The Investigator can withdraw a subject from the study if any of the withdrawal criteria is met.

Patients are free to withdraw from the study at any time upon request, without any consequence. Patients should be listed as having withdrawn consent only when they no longer wish to participate in the study and no longer authorize the investigators to make efforts to continue to obtain their outcome data. Every effort should be made to encourage patients to remain in the study for their planned outcome assessments. The patients should be told that their data are important for the scientific research even after they discontinue the drug product. If a patient is lost to follow-up, attempts to contact the patient should be made and documented in the patient's medical records.

